## **10.0 RISKS TO SUBJECTS**

The risks to human subjects include potential adverse effects of exercise. Risks of participation include tiredness from answering research questions or participating in exercise, anxiety about ability to read surveys or reach exercise goals, discouragement about ability to exercise, worry about loss of confidentiality/privacy, and perception of coercion to participate. Additional risks to participation include radiation exposure. There is minimal radiation exposure associated with a whole body DXA scan (<1  $\mu$ Sv), which is less than half of radiation received on a one-way trip from California to New York and has negligible health risks.

### **Adequacy of Protection Against Risks**

#### **a. Recruitment and Informed Consent**

The Oregon State Cancer Registry (OSCaR) will be used to recruit participants. Established in 1996, the registry is nationally recognized for the accuracy and completeness of its data. All tumors, except common skin cancers, are required to be reported by hospital registries, clinics, cancer treatment centers, and physician offices in Oregon and neighboring states where Oregon

residents are treated. Patient's data is reported, checked for quality assurance, and entered into OSCaR within six months of diagnosis. OSCaR procedures are well established and designed to protect persons in the registry. When each person's data is entered in the registry, the individual is sent a letter asking if he is willing to be contacted about opportunities to participate in research studies. Very few refuse to be contacted.

Patients will be identified by OSCaR for their cancer type, cancer treatment (surgery, radiation and/or chemotherapy), and zip code. OSCaR will then send identified patient data including the patient's physician information to our team using secure electronic transmission (i.e. encrypted flashdrive, secure encrypted email or stored on a secure shared drive such as Box). Data from OSCaR is only being used for purposes of identifying eligible patients and from this point forward is no longer involved in the research. Our team will then send an information letter about the study to listed physicians for identified persons in the registry, notifying the physician that their patient will be sent information about the study. Physicians who determine that their patients should not receive study information are asked to return a form to the study investigator within a 3-week period. These persons will no longer be considered eligible to receive study information. All other potential participants will be sent an information letter briefly describing the study along with a response form and contact information of the research team. Persons who are interested in receiving more information about the study are asked to either contact our team directly (phone, email, text) or complete the response form and return it to our team. For all response forms returned to our team and in response to all other forms of inquiry, a member of the research staff will then contact interested persons to provide more study information to them and to screen for eligibility if they indicate a willingness to participate. Participants will also be recruited via a study information mailing through the OHSU Cancer Registry and from various hospital systems such as Tuality Healthcare, Adventist Health, Providence, Legacy, Kaiser, and community oncology clinics such as Compass Oncology and interested participants will contact us if they would like to learn more about the study and to check for eligibility. Additional OHSU patients may be recruited by gathering patient demographic information from OCTRI's Cohort Discovery, OCTRI's Research Data Warehouse, and OHSU's Medical Records. Recruitments will occur via letters, e-mails, phone calls, or informational announcements through MyChart. In addition we will recruit at community events, such as patient conferences and fundraisers and through study advertisements placed through various media outlets (i.e., internet, newspaper, radio).

[name], all urologic oncologists with specialties in medical, surgical and radiation oncology, respectively, on the research team and co-investigators, will consult on eligibility issues as needed during recruitment. Eligible persons will come to the OHSU Knight Cancer Research Building to be consented and undergo baseline measures.

**Ancillary study:** In addition to the recruitment methods listed above, we will reach out to current and past study participants who have given their permission to be contacted about future study opportunities.

### **b. Protection Against Risk**

**Participant safety and side effects during exercise.** As with any form of exercise, there is a slight risk of injury. We have not had a single participant drop out of a study due to an injury related to the exercise program; however, as with any study in older adults, exercise adherence has been affected by minor musculoskeletal complaints and are typically exacerbations of pre-existing orthopedic conditions. We will take the following steps to reduce the risk of injury and symptoms/side from exercise training: 1) Physician clearance: We will send a notice to each participant's oncologist (or primary care provider) asking him or her to clear the participant for participation in physical performance testing and any of the study exercise programs prior to beginning exercise training. If a man's physician does not clear him for participation we will inform the participant and refer him to her physician for clarification of the decision, 2) Monitor for and treat early musculoskeletal symptoms: From experience in our prior trials we have developed an

injury prevention education and monitoring program. At the beginning of each participant's start in the intervention he is provided general injury prevention information from the Project Director and exercise trainer. During the intervention the exercise trainer will consult with the Project Director on any reported exercise-related injuries and/or physical complaints from participants that affects their ability to do their exercise program. The Project Director will consult with participants on an individual basis, as needed, and will advise on treatment of their injury/complaint and when referral to a health practitioner is appropriate. The Project Director will work with the study team to track minor and major complaints and injuries in order to evaluate the overall safety and appropriateness of the study interventions for the study population.

During testing visits, if a participant experiences tiredness, he will be told he can stop answering research questions, or participating in performance or clinical testing, and begin again at a later time. Surveys are administered electronically via a web-portal, unless a participant requests paper surveys (usually <5% of a sample). With on-line surveys participants can stop and restart surveys at their leisure, which can reduce tiredness and burden for participants. If tiredness occurs during exercise sessions, participants may rest as often as needed. If a participant is anxious about ability to read surveys, we will offer to ask the questions verbally and fill out the survey by telephone, if anxious about ability to reach exercise goals or discouraged about ability to exercise, Project Director, in consultation with the PI will problem-solve and support the participant in changing goals or developing alternative methods to meet goals. If a participant is worried about privacy and confidentiality of data, the Project Manager will discuss the methods for maintaining confidentiality: individual data will be identified only by a study ID number and only one computer file will link ID numbers with identifiable data; all computer records will be protected by a password known only to authorized study personnel; paper documents, such as surveys or computer disks, will be kept in locked files, and results will presented as group data only. To prevent the perception of coercion to participate, participants will be told they may decide to discontinue participation in the study at any time, that non-participation will not affect their usual care at their local clinic or at OHSU, and that data on non-participation will be kept confidential, using the methods described above.

To minimize risk against excess radiation exposure from DXA, whole body DXA scans will be conducted by a trained Research Assistant. Whole body DXA scans will be performed according to standard protocols which allows for early repositioning to minimize patient exposure.

During remote exercise and testing sessions, additional safety precautions will include: 1) Providing safety recommendations specific to exercises and/or assessments (i.e., standing near a wall for balance activities) 2) Adapting the exercise protocol as necessary (ie. limit weight.) 3) Verifying address of remote exercise location (i.e., home address), should the exercise instructor or Research Assistant need to call 911 in an emergency 4) Ensuring that emergency contact information is up-to-date and readily available.

Ancillary study: Participants in the ancillary study incur no risk from exercise.

## 11.0 POTENTIAL BENEFITS TO SUBJECTS

Participants may or may not personally benefit from being in this study.

## 12.0 TIMELINE & MILESTONES

Development	Y1				Y2				Y3				Y4				Y5			
	Q1	Q2	Q3	Q4	Q1	Q2	Q3	Q4	Q1	Q2	Q3	Q4	Q1	Q2	Q3	Q4	Q1	Q2	Q3	Q4
Finalize protocols, databases	X	X																		
Hire/train research assistants			X																X	
Hire/train exercise instructors			X			X				X					X					
Recruitment & initial testing																				
Recruit, enroll, baseline visit			W1		W2r	W3			W4r	W5			W6	W7	W8r					

Intervention and evaluation																			
Start 6-month intervention			W1		W2r	W3			W4r	W5		W6	W7	W8r					
Mid- & post-intervention visits			X	X	X	X	X	X	X	X	X	X	X	X					
6-month follow up visit					W1		W2r	W3			W4r	W5			W6	W7	W8r		
Data analysis & publication																			
Data cleaning and analysis						X	X	X	X	X	X	X	X	X	X	X	X	X	
Present and publish results																	X	X	

Participants are recruited in 8 waves (W1, W2, ...); "r" after wave abbreviation indicates a regional exercise site; Quarters are approximate time points

Ancillary study timeline:

Activity/Milestone	Y1			
	Q1	Q2	Q3	Q4
Develop ancillary project	X			
Enroll participants into ancillary study and collect data		X	X	
Ongoing data analysis (ADT, SmartSox, survey)		X	X	
Analyze data and submit manuscripts			X	X

## 13.0 BIO-STATISTICAL CONSIDERATIONS

### Power and Sample Size

We have powered the sample size based on our primary aim. In older adults, 20%-30% of community-dwelling elders are likely to fall within 1 year [11] and Li and others have reported a reduction in fall risk of 47% from 3 [86] or 6 [41] months of tai ji quan exercise. We are using an effect size for tai ji quan to power for both interventions because we have these data available from our prior work and effects sizes for strength training are similar to tai ji quan [87]. Our study will determine if strength training is as effective as tai ji quan. Using PASS 2008[88], based on a negative binomial regression model [89], at alpha = .05, the variance shared among the dummy vectors representing treatment ( $R^2=.25$ ), and an estimate of the overdispersion parameter (Phi) of 2.5, a sample size of n=300 (n=100 per group) participants will provide 80% power to detect at least a 47% reduction in the fall incidence rate over six months by being in either of the 2 exercise groups versus control. To protect against an estimated attrition of ~17% during the intervention period, 120 participants will be randomized per group (total sample size: N=360). The attrition estimate is conservatively based on the highest attrition rate from our prior strength training trials in prostate cancer survivors (0% and 16% attrition in 6 and 12 month trials, respectively [37, 39]). Though the total # of falls is the primary endpoint, the sample size of N=300 also provides sufficient power to detect differences between experimental and control groups on secondary outcomes of frailty and physical function. We and others' have data on the effect of exercise on individual components of frailty in prostate cancer survivors on ADT and self-report physical function. With a sample of N=100 per group we have a sufficient sample to detect a difference in 2.5% of lean body mass [90, 91], a 4 sec. faster chair stand time [37, 91], a 1.1 sec. faster gait speed [91], and a 9% difference in self-report physical function scores [37].

All analyses will retain each participant in the group he was randomly assigned regardless of missing data or drop out status (i.e., intention to treat). We will track medical treatment changes and disease progression during the study to describe the sample or justify why participants exited the study. In the unlikely event of a large subgroup, these data could be used for exploratory subgroup analysis to suggest directions for future research. Age, timing of ADT (current vs. past), fall history at enrollment and baseline frailty will be considered as possible covariates in all analyses. Age and timing of ADT (past vs current) are included since they may affect exercise tolerance and/or responsiveness to exercise training; fall history is included because we want to examine the efficacy of the interventions to reduce falls in men with a fall history and prevent falls

among men who have not recently fallen. Analyses will be conducted in Stata, R, and/or Mplus statistical software packages. Full information maximum likelihood estimation (FIMLE) will be used to estimate the models, as appropriate, because it is less biased and more efficient than other techniques for handling missing or incomplete data[92].

Aim 1: Compare the relative efficacy of tai ji quan and strength training to prevent falls: We will determine the efficacy of tai ji quan and strength training by comparing each of them to the control condition while adjusting for important covariates using negative binomial regression models which will analyze total number of falls per participant that occur from baseline to 6 months. A negative binomial regression was chosen over a Poisson regression for modeling the count data because of the overdispersion that is common with actual research data. [88, 93] Intervention type will be entered into the model as 2 dummy variables, with the reference group being the control group. This will allow a comparison of the each of the intervention groups against control. A *second* model will be run with strength training as the reference category to compare the intervention groups to each other. In addition to standard ITT analysis, the impact of participants who drop out of the study on the falls outcome will be examined in a secondary data analysis. A significant incidence rate ratio (IRR) less than 1.0 for the dummy vector representing tai ji quan and/or strength training would provide support for the hypothesis that the respective intervention reduced the rate of falls compared to the control group.

Aim 2: To determine and compare the efficacy of tai ji quan training and strength training to reduce frailty and dysfunction: Each participant will be classified as frail, pre-frail or robust based on his total frailty score (see **Measures**). We hypothesize that the number of men classified as frail or pre-frail will decrease over the course of the study in the tai ji quan and strength training groups compared to control. Formal tests of frailty hypotheses will be conducted in a generalized mixed effects modeling framework as implemented in the R statistical computing environment. [94] Frailty category will be the multinomial dependent variable (with “robust” as the reference group) and study time point (0, 3 and 6 mos.), group (control as the reference group) and the group x time interactions will serve as predictors. [95] We will also run a second model with strength training as the group reference category to compare the two experimental groups to each other. Significant group x time interactions will indicate that the distribution of frailty between the groups (e.g., tai ji quan vs. control) is different across time. For significant interactions, additional contrasts testing for frailty differences will be examined to describe the pattern of change across time. Group differences across time in the continuous physical function and individual frailty measures will be tested in a linear mixed effects modeling framework [94] to estimate the trajectory of change in each dependent variable across time for each individual in each group, and then comparing the average trajectories across groups. The primary effect of interest is a cross-level interaction. Specific hypotheses about treatment group effects will be specified by adding dummy variables and hypotheses will be tested through group x time interactions (as above). We will also evaluate the practical significance of the interventions by summarizing results with respect to effect size.

Aim 3: Determine how well the benefits of each intervention persist after structured training stops: We will use the same modeling strategies described above for each outcome (i.e., negative binomial regression, multinomial/linear mixed effects models). However, we will perform the analyses piecewise, with a change point occurring at 6 months. Of particular interest is whether the observed effects for the treatment groups differ or remain the same after the change point. In addition, we will examine whether participation in exercise following the end of the intervention moderates the persistent effect of the intervention on study endpoints. We will categorize the type of exercise participants engaged in (i.e., walking/aerobic, strength training, tai ji quan, stretching) for at least 50% of the follow-up period. These categories will then be dummy coded and entered into the analyses outlined above, along with the product of these dummy vectors and treatment to represent the interaction. A significant coefficient for the product term would indicate that continued exercise modifies the effect of the intervention on falls, frailty, or physical function. This

analysis will allow us to determine whether continued participation in an exercise program maintained improvements for an intervention group or a lack of participation caused a loss of improvements in an intervention group, and whether control participants who begin programs similar to the intervention programs improve in outcomes.

Exploratory Aim: Determine patterns and predictors of types of men who benefit the most. We will use a growth mixture modeling (GMM) approach using Mplus to explore there are distinct types of men (based on age, baseline frailty, cancer stage, ADT duration and timing, other treatments, etc.) who benefit most from the intervention(s). GMM is a type of clustering technique that can simultaneously handle longitudinal data and multiple measures to identify distinct subgroups of patients who have different responses to an intervention. For longitudinal outcomes (e.g., Aim 2), we will employ GMM to identify distinct patterns of change in subpopulations with varying response (growth) trajectories and unique variances reflecting homogenous within-trajectory growth. Patients will be assigned to the “most likely class” or pattern of change over time (e.g., men who improve most from an intervention) and follow-up analyses (e.g., multinomial regression) will be conducted to describe the demographic and clinical characteristics of patients who are classified into different subgroups.

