Androgen deprivation therapy (ADT) for prostate cancer increases the risk of falls and frailty, even if treatment stops. Recent evidence, including our data, indicates that prostate cancer survivors exposed to ADT are significantly more likely to report a history of falls, injurious falls, frailty and dysfunction compared to prostate cancer survivors never on ADT [4-9]. ADT is associated with muscle loss, weakness, fatigue, slowness, and inactivity [26-28] which are linked to falls in adults without cancer, and constitute the same elements of the Frailty Phenotype that predicts poor health outcomes [29]. New findings from our team and others show that the rate of falls, including those resulting in injury, are 2-3 times higher among prostate cancer survivors who receive ADT compared to men who never receive this treatment or to otherwise healthy, older men. In addition, our data indicate that prostate cancer survivors whether treated currently or in the past with ADT, have a 5 to 6-times higher risk of recurrent falls and 9 to 10 times higher risk of frailty than men never on ADT [8]. Nearly half of all prostate cancer survivors are treated with ADT [3], placing millions of men at increased risk for these subsequently life-threatening side effects.

Currently, clinical practice has no effective solution to the rising problems of falls and frailty from ADT. Despite the high risk associated with ADT, no fall or frailty prevention strategies, especially exercise-based modalities, have been developed in this clinical population and clinical guidelines are bereft of recommendations to manage these life-threatening consequences of treatment. Exercise has been shown to offer symptomatic relief from side effects of cancer treatment and improve quality of life among cancer survivors, but the potential benefits of exercise to prevent falls and frailty associated with ADT are unknown [30]. This creates a major treatment barrier in the field of oncology care for prostate cancer survivors as both the incidence of falls and prevalence of frailty increase as a result of conventional treatment with ADT. This dilemma makes the patient-oriented clinical treatment decisions difficult for providers and prolongs patient exposure to the harmful downstream consequences of ADT. Thus, there is an urgent clinical need to identify and test non-pharmacologic, community-based fall and frailty prevention programs for this at-risk patient population.

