## 5.0 INCLUSION/EXCLUSION CRITERIA

### Inclusion Criteria:

- Diagnosed with histologically confirmed prostate cancer (confirmed by self-report on Health History Questionnaire. In the case a participant isn't able to confirm this criterion, a letter will be sent to his physician.)
- Currently on ADT for  $\geq 6$  months OR not currently receiving ADT, but received  $\geq 6$ -month course within the last 10 years (confirmed by self-report on Health History Questionnaire. In the case a participant isn't able to confirm this criterion, a letter will be sent to his physician.)
- If they have had other treatment, such as surgery, radiation or chemotherapy, it must have been completed  $\geq 6$  weeks prior to enrollment and no concurrent adjuvant therapy other than ADT for prostate cancer (confirmed by self-report on Health History Questionnaire. In the case a participant isn't able to confirm this criterion, a letter will be sent to his physician)
- Meets criteria for having experienced  $\geq 1$  fall in the last year (confirmed by self-report on Health History Questionnaire) or if no falls, meets criteria for slow TUG time ( $\geq 12.0$  seconds) or slow chair stand time ( $\geq 10.0$  seconds) (confirmed by baseline screening testing)

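### The 80% power claim for falls needs about 1.1 falls per control man in six months; the plan states no such rate, and its own fall figures reach it only under favourable assumptions

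*Combined protocol and SAP*

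**What the plan says.** Section 13.0 (Power and Sample Size) opens its case with a general-population figure: "In older adults, 20%-30% of community-dwelling elders are likely to fall within 1 year". It takes a 47% reduction from earlier tai ji quan trials and applies it to both exercise arms. The calculation is "based on a negative binomial regression model [89], at alpha = .05", with R² = .25 among the treatment dummies and Phi = 2.5. From this the plan claims "80% power to detect at least a 47% reduction in the fall incidence rate over six months" with 300 men, 100 per group, "by being in either of the 2 exercise groups versus control". The primary analysis (Section 13.0, Aim 1) models the number of falls per man from baseline to six months.

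Section 5.0 admits ADT-treated men with at least one fall in the past year, "or if no falls, meets criteria for slow TUG time" or a slow chair stand. Section 1.0 reports that fall rates "are 2-3 times higher among prostate cancer survivors who receive ADT". The power paragraph uses neither fact.

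**The concern.** Power for a count endpoint depends directly on the control-arm mean, and the plan does not give one. The figure that stands in its place differs from the trial in three ways:

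- **Population:** general elders, against ADT-treated men selected for a fall or slow performance.
- **Window:** one year, against six months.
- **Measure:** proportion with any fall, against number of falls per man.

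So the 80% cannot be reproduced from the documents, and it is not evident that the quoted figure could yield it. This is the primary endpoint and the stated basis for N. If the true control rate is well below what the calculation needed, a null result would be read as a well-powered negative when it is not one.

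**Working it through.** **Can the 80% be reproduced?** No, because the control mean μ is missing. I solved for it instead.

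**Inputs from Section 13.0:** N = 300 in three equal arms (π = 1/3), rate ratio RR = 1 − 0.47 = 0.53, alpha .05, power 80%, Phi = 2.5, R² = .25. The cited method is the sample-size formula for Poisson regression (reference 89). R² = .25 is what two dummies for three equal arms give (correlation −0.5, squared), which supports this reconstruction. Two assumptions are mine: a two-sided test, and Phi as a multiplier of the Poisson variance.

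**Formula:** N = Phi × [z₀.₉₇₅√V₀ + z₀.₈₀√V₁]² / [μ (ln RR)² (1 − R²)]

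- V₀ = 1/[π(1 − π)] = 4.5
- V₁ = 1/(1 − π) + 1/(π RR) = 1.5 + 5.66 = 7.16
- Squared bracket: (1.960 × √4.5 + 0.842 × √7.16)² = 41.09
- (ln 0.53)² = 0.403
- μ = 2.5 × 41.09 / (300 × 0.403 × 0.75) = **1.13 falls per control man in six months**

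| Variant | Control mean needed for 80% |
|---|---|
| Two-sided, N = 300, R² = .25 | 1.13 |
| Pairwise, N = 200, no R² | 1.10 |
| One-sided, N = 300, R² = .25 | 0.91 |
| Two-sided, N = 300, R² dropped | 0.85 |
| Pairwise, N = 200, R² also applied (penalises twice) | 1.46 |
| No overdispersion (Phi = 1) | 0.45 |
| Phi as negative binomial dispersion, no R² | about 21 |

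**What the cited 20-30% gives.** A proportion p does not fix a mean, so I used two conversions to a six-month mean.

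- Poisson: −ln(1 − p)/2 = 0.11 to 0.18.
- Yearly variance 2.5 times the mean: the Poisson value × 1.5/ln 2.5 = 0.18 to 0.29.

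The two-sided requirement is about 4 to 10 times higher (1.13/0.29 and 1.13/0.11). Putting these means back into the formula, two-sided:

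| Basis | Falls per six months | Power |
|---|---|---|
| 20-30% alone | 0.11-0.29 | 21-37% |
| 2-3 fold applied to the mean | 0.22-0.88 | 31-71% |
| 3-fold applied to the proportion (90% fallers), Poisson | 1.15 | 80.5% |
| 3-fold on 30%, every man a prior faller | 1.15 | 80.5% |

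The 0.88 case tested one-sided gives 79%. The third row, converted with variance 2.5 times the mean instead, gives 1.88 falls and 94%. The other products of the multiplier and the proportion (40% or 60% fallers) stay at or below 0.75 falls and 65%.

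The last row assumes each man keeps a stable personal rate. The yearly mean is 3 × 0.584 = 1.752. The chance of no fall is 2.5^(−1.752/1.5) = 0.343. The mean given at least one fall is (1.752 − 0.343 × 1.752/2.5)/0.657 = 2.30 a year, or 1.15 per six months.

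A rough simulation (100 per arm, variance 2.5 times the mean, quasi-Poisson Wald test rather than the planned negative binomial model) gave about 74% power at 1.13 falls, so the formula is if anything slightly optimistic.

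**The case against.** The strongest reply is that the enrolled men are not general elders. Section 5.0 selects on a past fall or slow performance, and Section 1.0 also reports a 5 to 6 fold risk of recurrent falls with ADT, which matters for a count. This stands. The 21-37% describes men the trial does not enrol, and 0.9 falls is not a safe ceiling. The recurrent-fall multiple cannot be turned into a mean, however, because no baseline frequency is given.

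The conversion matters too. If the ratio of 2.5 describes six-month rather than yearly counts, and personal rates are stable, the yearly ratio is 1 + 2 × 1.5 = 4. Then 30% a year gives 0.3567 × 3/ln 4 = 0.77 falls a year, or 0.39 per six months (44% power). Among prior fallers only, it gives (0.772 − 0.7 × 0.772/4)/0.3 = 2.12 a year, or 1.06 per six months (78%), before any ADT multiplier. So strong enrichment could bring the rate near the requirement. But men without a fall may also enter, their share is not stated, and the plan makes none of these arguments.

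It can also be said that no arithmetic slip is shown and that restating design power now changes nothing: Section 4.0 already gives 284 men enrolled in the parent study, below the 300 in the calculation. Both facts are right. The restatement still governs how a null primary result is described.

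A reader might infer that the trial really has only 21-37% power, or that 80% is wrong. The documents support neither, since the fall rate in eligible men is not in them.

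**Conclusion.** The concern holds as a claim whose cited inputs do not deliver it. Under the cited method, 80% power needs about 1.1 falls per control man in six months (0.85 to 1.5 across sidedness, R² and pairwise variants). The quoted figure alone gives 21-37% power. With the protocol's ADT multiplier on the mean it gives 31-71% (79% at best if one-sided). With 2.5 taken as the yearly variance ratio, 80% is reached only by putting the full 3-fold multiplier on the top 30% and either applying it to the proportion or assuming every man is a prior faller.

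The 80% is therefore unsupported by the plan's own figures, not refuted. The result rests on a two-sided test, on Phi as a variance multiplier, and on converting a yearly proportion to a six-month mean. Confidence is medium for that reason. The absence of a control rate is certain.

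**What to change.** In Section 13.0, replace the general-elder sentence with the assumed six-month control-arm mean number of falls for men meeting Section 5.0, and its source. State whether alpha is one- or two-sided, and whether Phi multiplies the variance or is the negative binomial dispersion. Restate power at that rate. In place of a single 80%, show a range over about 0.2 to 1.2 falls per six months. With the inputs used above, power is 29% at 0.2, 57% at 0.6, 76% at 1.0 and 82% at 1.2.

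The pooled fall count, without arm labels, can be used to check the assumption without unblinding.

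The cost is one rewritten paragraph. The stated power will probably look less favourable. No extra patients are needed.
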